4.1.1 Screening Phase

The screening period is intended to allow determination of patient eligibility for the study. Screening will begin when the study informed consent form (ICF) is signed.

The patient must sign a study ICF on Day 1 of Screening. The ability of the patient to understand the consent form will be documented in the study ICF.

The Screening tests and evaluations must be completed within 4 weeks prior to enrollment. The required screening evaluations are outlined in the Schedule of Assessments (Table 1). Applicable evaluations from the last in-clinic visit in the Phase 1b/2a study WVE-HDSNP1-001 may be used if the last in-clinic visit occurred within 4 weeks prior to the Screening visit for this study (specified in Table 1). Screening assessments can occur over multiple days, provided they are within the Screening period. The Investigator will determine whether the patient meets eligibility criteria and will collect the demographic and medical data permitting full characterization of the patient. In addition, the Investigator should discuss the need for a legally authorized representative to provide consent on behalf of the patient in the event that the patient's cognitive capacity deteriorates during the course of the OLE study to the point that they are no longer able to consent. In addition, patients should identify a study partner (Section 4.1.1.1). These may or may not be the same person.

4.1.1.1 Study Partner

Patients should identify a study partner for the purposes of this trial. The role of the study partner will be to help ensure that the patient complies with study visits and assessments. Patients should have the same study partner throughout the course of the trial. The study partner must sign an acknowledgement of responsibilities form. The study partner does not have to be a legally authorized representative.

4.1.2 Treatment Phase

WVE-120101 will be administered monthly via IT dosing through Week 97. At each visit, patients will be evaluated for safety and tolerability. At the end of each 12-week period, patients will undergo assessments of clinical effects. A schedule of assessments is provided in [Table 1](#).

Up to 1 week before performing lumbar puncture for each dose, a blood sample will be tested locally for platelet count and prothrombin time to confirm that it is safe to proceed with the lumbar puncture ([Section 8.1.7](#)). Other predose assessments may also be performed up to 1 week before dosing as specifically listed in [Table 1](#).

At all dosing visits, patients should be monitored for a minimum of 4 hours postdose in the clinic. After the first dose only, a follow-up safety phone call will be performed on Day 2.

Immediately after study drug administration, all patients should be ambulatory for approximately 30 minutes postdose. Formal physical examinations targeting the neurological system will be performed at the time points noted in the Schedule of Assessments ([Table 1](#)).

Patients who are entering the study may be requested to consent to two additional lumbar punctures (LP) to provide CSF samples at two weeks after the first dose, and two weeks after the sixth dose to allow for more robust PK/PD modeling (see [Table 1](#) for more details). These additional CSF samples will be optional, and consent will be collected as a stand-alone question in the Informed Consent Form. If a patient has already passed the first dose, but not the sixth, and is willing to undergo the additional LP, then CSF will be collected 2 weeks after the sixth dose.

In addition to the above two CSF samples, patients at certain participating sites will undergo additional intensive PK blood and urine sampling as noted in [Table 2](#). This sampling will include additional time points for plasma and a 24-hour urine collection.

Dose Modifications

In the original OLE study protocol, patients who were in the 2 and 4 mg dose cohorts in the Phase 1b/2a study were enrolled into the 4 or 8 mg dose group in this study. Patients who were in the 8 and 16 mg dose cohorts in the Phase 1b/2a study were enrolled into the 8 or 16 mg dose groups, respectively in this study. As of this amendment, patients will receive 16 mg or a higher dose of WVE-120101 in this study. The maximum dose and frequency in this OLE study in a given country will not exceed the maximum dose and frequency described in the Phase 1b/2a

protocol (WVE-HDSNP1-001) approved in that country. If a dose lower than the maximum dose described in the Phase 1b/2a study is chosen for multiple dosing based on the safety review of the Phase 1b/2a study data by the Dose Escalation Committee (DEC) and Safety Monitoring Committee (SMC), that dose will be used in this OLE study.

Based on the SMC and DEC review of Phase 1b/2a safety data, the highest tolerated dose level and/or a lower dose level may be selected for multiple dosing and further evaluation in the OLE. If one dose level is selected, all patients will be switched to receive treatment at that dose level. If more than one dose is selected, patients will be randomized 1:1 to the highest tolerated dose and one lower dose to be determined by the DEC in agreement with the SMC. The randomization will be stratified by cohort and use a fixed block size. These doses may be further revised based on emerging safety, PD, or clinical effects data in the Phase 1b/2a study. The maximum dose and frequency in this OLE study will not exceed the maximum dose and frequency described in the Phase 1b/2a protocol (WVE-HDSNP1-001) approved in each country. For more details on additional dose modifications see [Section 4.1](#).

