In single and repeat-dose IT studies in rats and monkeys, transient, dose-dependent limb dysfunction was observed. In rats findings were observed at dose levels of 0.1 mg (human equivalent dose [HED] 56 mg) in a single-dose study and 0.05 mg (HED 28 mg) and above in repeat doses. These findings resolved within 72 hours. In monkeys, findings were observed at doses up to 6 mg (HED 67.2 mg). Over the course of 9 months in a chronic toxicity study in monkeys, affected animals at doses ≤ 2 mg experienced only 1 or 2 instances of limb dysfunction at sporadic time points. In monkeys, only the lower hind limbs were affected and findings were completely resolved within 48 hours post-dose. Due to their transience, lack of correlating histopathology, and lack of effect on the ability of animals to eat or ambulate, the findings were considered non-adverse.

Microscopic CNS findings were observed in both rats and monkeys after IT administration of WVE-120101. In rats, after 3 months of repeat IT dosing, cellular infiltrates, minimal to mild non-adverse spinal nerve root degeneration, and gliosis were observed. The findings were dose- and/or dose-concentration dependent, with minimal effects observed at 0.05 mg (dose concentration 2 mg/mL). In monkeys, after 3 to 9 months of repeat IT dosing, minimal to mild (3-month study) or minimal to moderate (9-month study) mononuclear cell infiltrates were observed at all doses evaluated. These findings were considered manifestations of the injection procedure and a general response to the immune-stimulating properties of the oligonucleotide^{17,18} and were considered non-adverse.

WVE-120101 demonstrated minimal potential for class effects associated with phosphorothioate oligonucleotides, such as systemic pro-inflammatory effects, activated partial thromboplastin time (aPTT) prolongation, hepatotoxicity, and nephrotoxicity^{18,19}. In addition, WVE-120101 was not associated with any other toxicities, including mutagenicity or effects on cardiovascular or respiratory function, and WVE-120101 exhibited minimal potential for off-target effects via bioinformatic analysis of the human genome.

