2.1 Rationale for the Doses, the Dosing Regimen, and Route of Administration

This is an open-label extension study for the Phase 1b/2a clinical study WVE-HDSNP1-001. The clinical starting dose in WVE-HDSNP1-001 was selected in consideration of the data from both single- and 13-week repeat-dose toxicology studies; an animal model possessing the SNP1 variant targeted by WVE-120101 was not available to the Sponsor. The clinical starting dose of 2 mg was based on the no-adverse-effect-level (NOEL) for transient limb dysfunction in monkeys, which is considered the most relevant species for the purposes of clinical assessment. The lack of findings in the monkey at a dose of 2 mg provides a 10-fold safety margin to the HED, on the basis of relative CSF volume. Subsequent doses are selected based on safety assessments from each cohort.

In the original OLE study protocol, patients who were in the 2 and 4 mg dose cohorts in the Phase 1b/2a study were enrolled into the 4 or 8 mg dose group in this study. Patients who were in the 8 and 16 mg dose cohorts in the Phase 1b/2a study were enrolled into the 8 or 16 mg dose groups, respectively in this study. As of this amendment, patients will receive 16 mg or a higher dose of WVE-120101 in this study. The maximum dose and frequency in this OLE study in a given country will not exceed the maximum dose and frequency described in the Phase 1b/2a protocol (WVE-HDSNP1-001) approved in that country. If a dose lower than the maximum dose described in the Phase 1b/2a study is chosen for multiple dosing based on the safety review of the Phase 1b/2a study data by the Dose Escalation Committee (DEC) and Safety Monitoring Committee (SMC), that dose will be used in this OLE study.

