Based on the SMC and DEC review of Phase 1b/2a safety data, the highest tolerated dose level and/or a lower dose level may be selected for multiple dosing and further evaluation in the OLE. If one dose level is selected, all patients will be switched to receive treatment at that dose level. If more than one dose is selected, patients will be randomized 1:1 to the highest tolerated dose and one lower dose to be determined by the DEC in agreement with the SMC (Figure 2). The randomization will be stratified by cohort and use a fixed block size. These doses may be further revised based on emerging safety, PD, or clinical effects data in the Phase 1b/2a study. The maximum dose and frequency in this OLE study will not exceed the maximum dose and frequency described in the Phase 1b/2a protocol (WVE-HDSNP1-001) approved in each country.

Dose modification will occur at the next scheduled visit from the date of implementation of this amendment (Amendment 1.0). In addition to the assessments performed at every dosing visit, the Unified Huntington's Disease Rating Scale (UHDRS) and clinical laboratory evaluations should be performed at the visit when a dose is changed. Patients will not be asked to restart the treatment phase but will continue to receive doses as originally scheduled, every 4 weeks, at the new dose level.

Figure 2 Dose Modification Scheme

Abbreviations: DEC=Dose Escalation Committee; SMC=Safety Monitoring Committee

*Dose modification randomization. Applicable if 2 doses are studied.

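### The Day 2 safety call is tied to the first OLE dose, so patients stepped up to 16 mg or more have no scheduled next-day contact at the new dose (minor)

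*Combined protocol and SAP*

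**What the plan says.** Section 4.1.2 requires at least 4 hours of clinic monitoring at every dosing visit and then adds one further contact: "After the first dose only, a follow-up safety phone call will be performed on Day 2". Footnote d of Table 1 confirms that this is a telephone contact.

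Section 4.1 (Dose Modifications) says that patients originally entered the OLE at 4, 8 or 16 mg and, as of the amendment, receive 16 mg or more. The schedule does not start again: "Patients will not be asked to restart the treatment phase but will continue to receive doses as originally scheduled, every 4 weeks". On top of the routine dosing-visit assessments, a dose change adds two items: the UHDRS and "clinical laboratory evaluations should be performed at the visit when a dose is changed". Footnote b of Table 1 repeats this. If two dose levels are chosen, "patients will be randomized 1:1 to the highest tolerated dose and one lower dose". Section 2.1 also allows later up- or down-titration at cohort level.

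On the acute risk, Section 1.3 states: "In single and repeat-dose IT studies in rats and monkeys, transient, dose-dependent limb dysfunction was observed". It gives resolution within 72 hours in rats, and for monkeys: "In monkeys, only the lower hind limbs were affected and findings were completely resolved within 48 hours post-dose".

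**The concern.** The protocol gives a patient a next-day call at the first OLE dose but none when the dose is later doubled or quadrupled. The 4-hour stay, the 24-hour telephone number and the instruction to report symptoms apply equally at the first dose, where a call is still added.

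The stake is patient safety and the quality of AE records, not a statistical test. Section 9.1 asks for the date and time of onset and resolution of each AE. A short motor symptom that appears after the patient leaves the clinic at a new dose, and that the patient does not report, would first be asked about weeks later. Patients with HD may have cognitive impairment, so recall over that interval may be poor.

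**Working it through.** The plan gives no figure to reproduce here. The check sets the provisions side by side, with some simple arithmetic. It relies on the prose and footnotes, because the columns of Table 1 are not reliably aligned in the text available.

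**Does a dose change trigger the call?** The call is limited to the first dose (4.1.2). A dose change does not restart the treatment phase (4.1). The additions at a dose change are the UHDRS and clinical laboratory tests (4.1; Table 1, footnote b). No other section adds a next-day contact. The answer is no.

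**Can the two added assessments detect a reaction to the new dose?** Footnote f allows both up to 1 week before dosing, and footnote e puts the clinical effects scales before other assessments that day. They are not designed to observe what follows the new dose.

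**Size of the step** (doses from 4.1):
- 8 to 16 mg: 16/8 = 2-fold
- 4 to 16 mg: 16/4 = 4-fold
- Larger if the selected dose is above 16 mg; the OLE protocol does not state such a dose.

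**Time to the next scheduled contact** (4-week interval from 4.1; ±1-week windows from Table 1):
- Nominal: 28 days
- Shortest: 28 − 7 − 7 = 14 days
- Longest: 28 + 7 + 7 = 42 days
- Pre-dose tests may be done up to 7 days before dosing (4.1.2; footnote f), so nominally from 28 − 7 = 21 days.

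**Visits that could shorten this by coincidence:**
- The optional CSF visit follows the first or sixth dose by 14 days (footnote c). The sixth dose falls at Week 1 + 5 × 4 = Week 21.
- Intensive-PK patients have a 24-hour sample at Week 73 and a visit 7 days later (Table 2).
- Neither is linked to a dose change.

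**Where a next-day call would fall.** The last scheduled check is the targeted motor examination at 4 hours (footnote h). Animal limb findings resolved within 48 hours (monkeys) or 72 hours (rats). A call at about 24 hours lies inside both periods. If a human event followed that time course (an assumption), it would be over 28 − 2 = 26 or 28 − 3 = 25 days before the next nominal dosing visit.

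**Human experience at the new level.** At the cutoffs in Section 1.4, single doses had reached 16 mg and multiple doses 4 mg. The minimum new repeat dose is therefore 16/4 = 4 times the highest multiple dose then reported.

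**The case against.** A first-dose-only call is a coherent choice. The protocol does not say why the call exists. The parent study was placebo-controlled (Section 1.4), so the first OLE dose may be some patients' first active exposure, whereas patients at a later dose change have already received the drug. Section 1.4 reports no stopping criteria met, no related SAEs, and no related TEAEs in the spinal cord and nerve root group. The animal findings were rated non-adverse. The 1- and 4-hour motor examinations target the relevant sign, which a telephone call cannot examine. Patients are told to report symptoms and have a 24-hour number (Sections 9 and 9.1). Dose levels are set after DEC and SMC review. One call does not cover the first week or two in which Section 2.1 says AEs tend to occur.

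Most of this stands, and it limits the gain. It explains a call at the first dose, but not why one is unnecessary at a step-up. The symptom instruction and the telephone number depend on the patient acting. SMC review of this study ends when the parent study is complete (Section 4.4), which is also when Section 2.1 foresees further dose adjustment.

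Three stronger readings are tempting, and the documents do not support them.
- *Patients go unmonitored for four weeks.* They do not: the safeguards above apply, and pre-dose testing can bring contact forward.
- *The animal safety margin is nearly used up at 16 mg.* Section 2.1 says "The lack of findings in the monkey at a dose of 2 mg provides a 10-fold safety margin to the HED", and a reader might scale that down. But Section 1.3 reports affected monkeys at 2 mg or below in the 9-month study, so 2 mg is not a clean reference for chronic dosing. Scenarios above 16 mg would rest on doses that the OLE protocol does not state.
- *The omission is an inconsistency, or it biases an analysis.* No provision is contradicted, and no bias in a stated analysis is shown.

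**Conclusion.** The gap holds as a minor, inexpensive improvement to safety monitoring. Patients raised from 4 or 8 mg to 16 mg or more, or up-titrated later, have no scheduled next-day contact at the new dose, apart from chance overlap with an intensive-PK visit. Patients who first enter at 16 mg or more do get the call at that dose.

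Confidence is high that the contact is absent and lower on how much a call would add. The benefit rests on two assumptions: that a short post-dose event in patients could resemble the animal findings in timing, and that some such events would not be reported spontaneously. The documents do not give the number of patients already on 4 or 8 mg; planned enrolment of about 50 is the ceiling.

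**What to change.** In Section 4.1.2, replace the first-dose-only condition with: *After the first OLE dose and after the first dose following each dose modification or dose-level randomization, a safety phone call will be made the next day.* Use the existing AE and concomitant-medication questions. Mark the call in the Dose Modification column of Table 1 and extend footnotes b and d to match. If the first OLE dose and the dose assignment coincide, one call serves both.

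Where patients are randomized 1:1 to two doses, call everyone in that step, including those whose dose is unchanged or lowered. Section 10.4.2 presents AEs by dose group, and calling only patients whose dose rises could make AE solicitation differ between the randomized groups.

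The cost is one short call by existing site staff per patient per step, at most about 50 calls per step, plus the edits to the text and Table 1. No dose rule or clinic procedure changes.

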4.1.3 Follow-Up Visit

All patients are required to complete follow-up assessments, including evaluations of safety, PD, PK, and clinical effects ([Table 1](#)). Patients will be followed until Week 101 (4 weeks after the last dose). An early termination (ET) visit will be required in the event of early withdrawal.

4.1.4 Early Treatment Withdrawal and Early Termination

If a patient withdraws from treatment, but wishes to remain in the study, the patient should continue with all planned visits and applicable assessments. PK assessments as well as lumbar punctures (with associated labs) will no longer be necessary unless a patient agrees to allow for one final lumbar puncture. A urine pregnancy test should be completed on the visit after the last dose of treatment.

If a patient withdraws from the study, the patient should complete an early termination visit ([Table 1](#)).

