4 STUDY DESIGN

4.1 Study Design Overview

[figure not shown]
This is an OLE study to evaluate the safety, tolerability, PK, PD, and clinical effects of WVE-120101 in adult patients with early manifest HD who carry a targeted single nucleotide polymorphism, SNP1. The planned duration of this study is approximately 101 weeks. To participate in the study, patients must have completed their Day 168 or 196 (depending upon dosing cohort and requirements in a given country) of the parent Phase 1b/2a clinical study [WVE-HDSNP1-001](#).

Screening may last up to 4 weeks. Patients will be dosed on Day 1 with WVE-120101 administered via the IT route and stay in the clinic for monitoring through 4 hours postdose.

Patients will return to the clinic every 4 weeks for dosing visits and safety monitoring. Every 12 weeks, patients will undergo assessments of clinical effects. After the last dosing visit (Week 97), patients will return for 1 follow-up safety visit at Week 101.

A schematic of the overall study design and timing is provided in [Figure 1](#).

Figure 1 Schematic of Study Design

[figure not shown]
Dose Modifications

In the original OLE study protocol, patients who were in the 2 and 4 mg dose cohorts in the Phase 1b/2a study were enrolled into the 4 or 8 mg dose group in this study. Patients who were in the 8 and 16 mg dose cohorts in the Phase 1b/2a study were enrolled into the 8 or 16 mg dose groups, respectively in this study. As of this amendment, patients will receive 16 mg or a higher dose of WVE-120101 in this study ([Figure 2](#)). The maximum dose and frequency in this OLE study in a given country will not exceed the maximum dose and frequency described in the Phase 1b/2a protocol (WVE-HDSNP1-001) approved in that country. If a dose lower than the maximum dose described in the Phase 1b/2a study is chosen for multiple dosing based on the safety review of the Phase 1b/2a study data by the Dose Escalation Committee (DEC) and Safety Monitoring Committee (SMC), that dose will be used in this OLE study.

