4.2 Schedule of Assessments

The schedule of assessments is provided in [Table 1](#). The schedule of additional assessments for patients undergoing intensive PK assessments is provided in [Table 2](#).

Table 1 Schedule of Assessments

Timing of Assessment (Visit Window, if applicable) Event/Assessment	Screening ^a		Treatment							Follow-up	ET
	Wk -4 to Wk -1	Wk 1	Wk 5 (±3 days)	Wks (±1 Wk)	Wks (±1 Wk)	Wks (±1 Wk)	Wk 97 (±1 Wk)	Dose Modification Assessments ^b	Additional CSF Collection ^c (Optional)	Wk 101 (±1 Wk)	
				9	13	25					
				17, 21	37	49					
				29, 33							
				41, 45	61	73					
				53, 57							
				65, 69							85
77, 81											
89, 93											
Patient ICF signed	X										
Inclusion/exclusion criteria	X										
Drug screening	X										
Medical history and demographics	X										
C-SSRS ^{e,f}	X	X	X	X	X	X	X			X	X
UHDRS ^{e,f}		X	X		X	X	X	X		X	X
PBA-s ^{e,f}		X	X	X	X	X	X			X	X
Physical examination ^{a,g}	X	X		X	X	X	X			X	X
Targeted postdose physical examination of motor effects ^h		X		X	X	X	X				
Serum pregnancy test ⁱ	X										
Urine pregnancy test ⁱ		X		X	X	X	X				
Adverse event monitoring	X	X	X	X	X	X	X		X	X	X

Timing of Assessment (Visit Window, if applicable) Event/Assessment	Screening ^a		Treatment							Follow-up	ET
	Wk -4 to Wk -1	Wk 1	Wk 5 (±3 days)	Wks (±1 Wk)	Wks (±1 Wk)	Wks (±1 Wk)	Wk 97 (±1 Wk)	Dose Modification Assessments ^b	Additional CSF Collection ^c (Optional)	Wk 101 (±1 Wk)	
				9	13	25					
				17, 21	37	49					
				29, 33							
				41, 45	61	73					
				53, 57							
				65, 69							85
Day -28 to Day -1	Day 1	Day 2 ^d	77, 81								
			89, 93								
Prior and concomitant medications	X	X	X	X	X	X	X	X	X	X	
Blood pressure/pulse ^j	X	X	X	X	X	X	X	X	X	X	
Temperature	X	X	X	X	X	X	X	X	X	X	
Weight ^{a,f}	X	X				X	X		X	X	
Height	X										
Electrocardiogram ^k	X					X					
Pre-LP PT and platelet ^{f,l}		X	X	X	X	X	X	X			
Clinical laboratory evaluations ^{a,f,m}	X	X	X	X	X	X	X	X			
Urine dipstick ^{a,f,m}	X	X			X	X	X		X	X	
Blood sample for PK ⁿ		X	X			X					
Blood sample for immunogenicity		X	X			X					
CSF sample for safety, exposure, and PD ^o		X	X	X	X	X	X	X			
Brain magnetic resonance imaging (MRI) ^p	X					X	X			X ^q	

Timing of Assessment (Visit Window, if applicable) Event/Assessment	Screening ^a		Treatment						Follow-up	ET
	Wk -4 to Wk -1	Wk 1	Wk 5 (±3 days)	Wks (±1 Wk)	Wks (±1 Wk)	Wks (±1 Wk)	Wk 97 (±1 Wk)	Dose Modification Assessments ^b	Additional CSF Collection ^c (Optional)	Wk 101 (±1 Wk)

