				9	13	25				
				17, 21	37	49				
				29, 33	61	73				
	Day -28 to Day -1	Day 1	Day 2 ^d	41, 45	85	85				
				53, 57						
				65, 69						
77, 81										
89, 93										
Study drug administration via IT injection ^r	X		X	X	X	X	X			

Abbreviations: CSF = cerebrospinal fluid; C-SSRS = Columbia-Suicide Severity Rating Scale; ET = early termination; h = hour; ICF = informed consent form; IT = intrathecal; LP= lumbar puncture; PBA-s = Short Problem Behaviors Assessment; PD = pharmacodynamics; PK = pharmacokinetics; PT = prothrombin time; UHDRS = Unified Huntington’s Disease Rating Scale.

^a If Screening is within 4 weeks of the completion of the Phase 1b/2a study, the values from the final visit in the parent study can be used for this assessment.

^b Dose modification will occur at the next scheduled visit from the date of implementation of this amendment (Amendment 1.0). In addition to the assessments performed at every dosing visit, the UHDRS and clinical laboratory evaluations should be performed at the visit when a dose is changed. See [Section 4.1](#) for more details.

^c Collect CSF 14 days (± 3 days) after the first dose and 14 days (± 3 days) after sixth dose. Patients should be monitored after the lumbar puncture per institutional standards.

^d This visit will be a phone call.

^e Clinical effects measures and C-SSRS should be performed prior to any other assessments that day.

^f This assessment can be done up to 1-week predose, at each applicable dosing visit.

^g Physical examination includes (at a minimum): head, eyes, ears, nose, throat, respiratory, cardiovascular, gastrointestinal, musculoskeletal, psychiatric, and neurologic systems. For dosing days, physical examination should be done before the dose is given.

^h Targeted postdose physical examination to assess potential motor effects focuses on the neurologic system, with special attention to the motor system, upper and lower extremity measures of strength, tone, reflexes, and ambulation. This should be performed at 1 and 4 hrs postdose (± 15 mins).

ⁱ Negative serum pregnancy test documented at Screening for female patients. Negative urine pregnancy test documented predose for female patients.

^j Blood pressure (systolic and diastolic) and pulse: measured ≤30 mins predose and 4 hours (±15 mins) postdose at each dosing visit. Patient must rest quietly for ≥3 minutes prior to measuring.

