5.1 Inclusion Criteria

1. Patient has documented ability to understand the written study ICFs and has provided signed written informed consent prior to any study procedures.
2. Patient successfully completed their Day 168 or 196 visit (depending upon dosing cohort and requirements in a given country) of the Phase 1b/2a study with WVE-120101, [WVE-HDSNP1-001](#).
3. In the opinion of the Investigator, the patient is able to tolerate all study procedures, is willing to comply with all other protocol requirements, and tolerated study drug in the parent study.
4. Patient is willing to practice highly effective contraception for the duration of the study if patients or their partners are of childbearing potential. Non-childbearing potential and highly effective methods of contraception are defined in the protocol ([Section 5.2.1](#)).

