8.1.10 Pregnancy Testing

For female patients of childbearing potential, a negative serum pregnancy test must be documented at the Screening Visit and a negative urine pregnancy test must be documented at the times noted on the Schedule of Assessments (Section 4.2). The serum pregnancy test will be determined by a central lab; urine pregnancy tests will be performed locally.

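### Women who complete dosing have no pregnancy test scheduled after their last dose, although Section 4.1.4 asks for one in patients who stop treatment early and stay in the study

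*Combined protocol and SAP*

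**What the plan says.** Section 4.1 fixes the end of the study for completers: "After the last dosing visit (Week 97), patients will return for 1 follow-up safety visit at Week 101". Section 4.1.3 confirms that Week 101 falls 4 weeks after the last dose and sends the reader to Table 1 for the follow-up assessments.

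Section 4.1.4 has two paragraphs. The first concerns patients who give up treatment but remain in the study, and it ends: "A urine pregnancy test should be completed on the visit after the last dose of treatment". The second concerns patients who leave the study: "If a patient withdraws from the study, the patient should complete an early termination visit". It refers to Table 1 and does not mention pregnancy testing.

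In Table 1 (Section 4.2), the row "Urine pregnancy test" is marked at dosing visits and has no mark under Week 101 or ET. Footnote i describes the timing: "Negative urine pregnancy test documented predose for female patients". Section 8.1.10 sets no timing of its own; it says "a negative urine pregnancy test must be documented at the times noted on the Schedule of Assessments". Section 9.5 requires any pregnancy during the study to be reported and followed to its outcome, but schedules no test. On prevention, Section 5.1 requires the following of patients where they or their partners are of childbearing potential: "Patient is willing to practice highly effective contraception for the duration of the study".

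**The concern.** The protocol accepts that a woman who stops treatment early should be tested at the next visit. The same reasoning applies to a woman who finishes. She has had the most doses: one every 4 weeks from Week 1 to Week 97, which is (97 − 1)/4 + 1 = 25. The documents give no reason for treating her differently.

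Each earlier dosing interval is closed by the predose test for the next dose. The last interval has no next dose, so nothing closes it. A very early pregnancy could test negative before the Week 97 dose, or begin afterwards, and Week 101 is the last scheduled visit at which it could be found. The follow-up required by Section 9.5 depends on the pregnancy being recognised.

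Only detection is at stake. No dose follows Week 101, so no dosing decision depends on the missing test.

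**Working it through.** **1. Which patients are covered**

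| Patient path | Visit after last dose | Test set by the text? | Marked in Table 1? |
|---|---|---|---|
| Stops treatment, stays in study | Next planned visit | Yes, Section 4.1.4, first paragraph | Not at a visit without dosing (footnote i: predose only) |
| Completes dosing at Week 97 | Week 101 | No | No |
| Leaves directly from dosing | ET | Only if the 4.1.4 sentence is read to reach ET | No |

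A patient who stops treatment, attends a further visit and leaves later has already been tested under Section 4.1.4. ET is therefore the smaller part of the point.

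**2. Can the table be trusted here?** The table is partly damaged in the text available. The headers imply 12 columns: Screening, Day 1, Day 2, Week 5, three groups of weeks, Week 97, Dose Modification, Additional CSF, Week 101 and ET. The rows on the relevant page show 11 cells, with Day 2 and Week 5 apparently merged.

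- Urine pregnancy test row: blank, X, blank, X, X, X, X, blank, blank, blank, blank.
- C-SSRS, UHDRS, PBA-s, physical examination and AE monitoring rows on the same page all end in X, X, under Week 101 and ET.
- The targeted postdose motor examination, which belongs to dosing visits only, has the same pattern as the pregnancy row.

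With the 11-cell reading, Week 97 is cell 7 and Week 101 is cell 10. The last X in the pregnancy row is in cell 7, so a displacement of 10 − 7 = 3 cells would be needed to put it at Week 101. Footnote i points the same way, since a predose test cannot belong to a visit without a dose.

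**3. Length of the untested interval**

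- Nominal: (101 − 97) × 7 = 28 days.
- Both visits have a window of ±1 week (Table 1). If both are anchored to Day 1: 28 − 14 = 14 days to 28 + 14 = 42 days.
- If Week 101 is anchored to the actual last dose: 28 − 7 = 21 days to 28 + 7 = 35 days.

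The protocol does not state the anchor.

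**4. Expected conceptions in the interval**

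Formula: number of women of childbearing potential × annual failure rate × days/365.

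Inputs are approximately 50 patients (Section 5) and a contraceptive failure rate below 1% per year (Section 5.2.1.2). The number of women of childbearing potential is not given, so 50 is taken as the ceiling and 25 as an illustration. The 5% rate is an assumption for imperfect use and is not in the documents.

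| Women | Rate per year | Days | Expected conceptions |
|---|---|---|---|
| 50 | below 1% | 28 | below 50 × 0.01 × 28/365 = 0.038 |
| 50 | below 1% | 42 | below 50 × 0.01 × 42/365 = 0.058 |
| 25 | below 1% | 28 | below 25 × 0.01 × 28/365 = 0.019 |
| 50 | 5% (assumed) | 28 | 50 × 0.05 × 28/365 = 0.19 |
| 25 | 5% (assumed) | 28 | 25 × 0.05 × 28/365 = 0.096 |

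These figures leave out conceptions shortly before Week 97 that the predose test missed. They include conceptions too recent for a urine test to detect at Week 101.

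**The case against.** **The row may have lost a mark.** The study drug row shows five marks after Day 1 (Week 5, three groups of weeks, Week 97), and footnote i ties the test to dosing, so the pregnancy row should also have five. It has four. Either a mark was lost in extraction or the table omits a predose test at a dosing visit. This is a fair reason to check the row against the PDF. The discrepancy concerns the Day 2/Week 5 position, however, and neither explanation puts a mark at Week 101. If cell 3 were Day 2 alone, the remaining marks would end earlier than Week 97, not later.

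**Section 4.1.4 could be read more widely.** The sentence on the test does not itself say that it is limited to early withdrawal, and for a completer the visit after the last dose is Week 101. The heading and paragraph make the narrow reading more natural. On the wide reading, Table 1 and footnote i omit a required test, and Section 8.1.10 sends sites to that table. Both readings call for the same correction.

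**The gain is very small and no stated requirement is breached.** This stands. Contraception is required throughout, adverse events are asked about at every visit, patients have a 24-hour telephone contact (Section 9.1), and the plasma half-life in animals is under 24 hours (Section 2.1).

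**A change has procedural cost.** This also stands. Section 14.3.1 sends amendments beyond minor clarifications to ethics committees and regulators, and under Section 11.4 a revised consent form must be signed again by active patients.

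**Conclusion.** The point holds as a minor gap in the safety schedule: no pregnancy test is set after the last dose for completers, and none is marked at ET. The untested interval for completers is 28 days nominal, with a range of 14 to 42 days or 21 to 35 days depending on how the visit windows are anchored. Expected conceptions in 28 days are below 0.04 at the protocol's own failure rate with all of the approximately 50 patients counted, and about 0.19 at the assumed 5% per year. The sample size, endpoints, analysis populations and model results are unaffected.

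The conclusion rests on the narrow reading of Section 4.1.4 and on the Week 101 and ET cells of Table 1 being blank in the original as they are in the text available. It is an improvement worth making because it is cheap and extends a rule the protocol already contains. It is not a reason to delay the study.

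**What to change.** For female patients of childbearing potential:

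- Mark the local urine pregnancy test in Table 1 at Week 101, and at ET when no test has been done since the last dose.
- Add both time points to footnote i, which now covers predose testing only.
- In Section 4.1.4, state that the test at the visit after the last dose applies to completers, to patients who stop treatment but stay, and to patients who leave the study.
- While editing the row, check its Week 5 cell against the original table, since Week 5 is a dosing visit.

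The text change is two table cells, one footnote and one sentence. For completers, the burden is one extra local urine test at a visit already scheduled, where Table 1 also lists a urine dipstick. Because the change adds a procedure, it is best carried in the next amendment made for other reasons, so that ethics and regulatory submission, and any re-consent, are not incurred for this alone.
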